Study I8K-JE-JPDB (JPDB) is the first clinical evaluation of LY3337641 in Japanese subjects and is being conducted to assess the safety, tolerability, pharmacokinetics (PK), and pharmacodynamics (PD) of single-dose (SD) and multiple-dose (MD) administration of LY3337641 in healthy Japanese and Caucasian subjects. Findings from the study will be used to assess the safety and tolerability of LY3337641 in this study population including Japanese subjects, further characterize the PK properties of LY3337641, and explore the PD effects of Bruton's tyrosine kinase inhibition. Such findings in Japanese subjects are essential for further clinical development in Japan for various indications.

Objectives/Endpoints:

| Objectives | Endpoints |
|------------------------------------------------------------------------------------------------------------------------------------------------------------------------------|-------------------|
| 
Primary To explore the safety and tolerability of LY3337641 in healthy Japanese and Caucasian subjects
 | AEs and SAEs |
| 
Secondary To estimate the PK parameters of single and multiple doses of LY3337641 following oral administration in healthy Japanese and Caucasian subjects
 | C_{max} and AUC |

Abbreviations: AEs = adverse events; AUC = area under the plasma concentration-time curve; C_{max} = maximum drug concentration; PK = pharmacokinetic; SAEs = serious adverse events.

Summary of Study Design:

Study JPDB is a single-site, subject- and investigator-blind, randomized, placebo-controlled, SD and MD study to assess the safety, tolerability, PK, and PD of LY3337641 in healthy Japanese and Caucasian subjects.

Treatment Arms and Duration:

Screening may occur up to 28 days prior to the first dose (Day 1). All cohorts will be randomized in a 3:1 ratio of LY3337641 to placebo. Study JPDB will numerically compare LY3337641 (30 mg once daily in MD cohorts and 5, 80, and 160 mg in SD cohorts) with placebo, when administered orally. An optional cohort may be included in the MD portion. The study drug is supplied as tablets containing 5 or 20 mg of LY3337641 with matching placebo tablets. For the MD cohorts, 6 Japanese subjects and 3 Caucasian subjects will receive LY3337641, while 2 Japanese subjects and 1 Caucasian subject will receive placebo. For the SD cohorts, 3 Japanese subjects and 3 Caucasian subjects will receive LY3337641, while 1 Japanese subject and 1 Caucasian subject will receive placebo.

In the MD cohorts, LY3337641 or placebo will be dosed on Days 1 through 15, and subjects will be followed for approximately 2 weeks. In the SD cohorts, LY3337641 or placebo will be dosed on Day 1, and subjects will be followed for approximately 2 weeks.

Number of Subjects:

Up to 60 subjects may be enrolled so that approximately 36 to 48 subjects complete the study.

Statistical Analysis:

PK analyses will be conducted for all subjects who receive at least 1 dose of LY3337641 and have evaluable PK data. PD analyses will be conducted on the full analysis set, which includes all data from all subjects receiving at least 1 dose of LY3337641 or placebo. Safety analyses will be conducted for all randomized subjects who receive at least 1 dose of LY3337641 or placebo and have at least 1 postdose safety assessment, regardless of whether they have completed all protocol requirements. For QT interval, all subjects with at least 1 postdose QT interval measurement will be included in the analysis. Summary statistics, data tabulations, and data graphs will be provided and may be separated by race (Japanese and Caucasian) as appropriate.

Safety: All adverse events will be listed, and if the frequency of events allows, safety data will be summarized using descriptive methodology. The incidence of symptoms for each treatment will be presented by severity and by association with the investigational product as perceived by the investigator. Symptoms reported to occur prior to enrollment will be distinguished from those reported as new or increased in severity during the study. Each symptom will be classified by the most suitable term from the medical regulatory dictionary. The number of investigational-product-related serious adverse events will be reported. Laboratory parameters, vital signs, and electrocardiogram parameters will be summarized using standard descriptive statistics.

PK Analysis: PK parameter estimates for LY3337641 will be calculated using standard noncompartmental methods of analysis. In the SD cohorts, the primary parameters for analysis will be maximum drug concentration (C_{max}), area under the concentration versus time curve from zero to infinity ($AUC_{0-\infty}$), and area under the concentration versus time curve from 0 to 24 hours (AUC_{0-24}) of LY3337641. In the MD cohorts, the primary parameters to be calculated will include C_{max} (or C_{max} during a dosing interval at steady state [$C_{max,ss}$]) and area under the concentration versus time curve during the dosing interval ($AUC_{0-\tau}$) of LY3337641 after the first and last dose of investigational product. Other noncompartmental parameters, such as half-life, apparent clearance, apparent volume of distribution, and accumulation ratio (MD period only), may be reported.

PD Analysis: Bruton's tyrosine kinase occupancy will be listed and summarized using standard descriptive statistics.

2. Schedule of Activities

Study Schedule Protocol I8K-JE-JPDB (Cohorts 1 and 5)

| Visit | Screening | Treatment Period ^a | | | | | | | | | Follow-Up ^a | | | | |
|-------------------------------------------------------------------------|-----------|-------------------------------|----|-------------------------------------|-----------------|---|---|----|---------------------------|----|------------------------|----|----|----|------------|
| Study Day | ≤28 days | -2 | -1 | 1 ^b | 2 | 4 | 8 | 11 | 15 | 16 | 17 | 19 | 22 | 25 | 29/ EoS |
| Inpatient stay at CRU | | ←—————→ | | | | | | | | | | | | | |
| Informed consent | X | | | | | | | | | | | | | | |
| Review eligibility | X | | X | | | | | | | | | | | | |
| Randomization | | | | X | | | | | | | | | | | |
| IP administration ^c | | | | X | X | X | X | X | X | | | | | | |
| Complete medical history | X | | | | | | | | | | | | | | |
| Review preexisting conditions/AEs ^d | X | X | X | X | X | X | X | X | X | X | X | X | X | X | X |
| Review concomitant medications ^d | X | X | X | X | X | X | X | X | X | X | X | X | X | X | X |
| Complete physical examination | X | | | | | | | | | | X | | | | X |
| Symptom-directed physical examination ^d | | X | X | X | X | X | X | X | X | X | | X | X | X | |
| Body weight and height ^e | X | | X | | | | | | X | | | | | | X |
| Vital signs (pulse rate, blood pressure, body temperature) ^f | X | | 0 | 0, 1, 2, 4, 12 | 24 ⁱ | 0 | 0 | 0 | 0, 1, 2, 4, 12 | 24 | 48 | | | | X |
| 12-Lead ECGg | X | | | -1, -0.5, 0, 0.5, 1, 2, 3, 4, 6, 12 | 24 ⁱ | 0 | 0 | 0 | 0, 0.5, 1, 2, 3, 4, 6, 12 | 24 | 48 | | | | X |
| Chest x-ray (posterior, anterior, and lateral) | X | | | | | | | | | | | | | | |
| Clinical laboratory measures (serum chemistry, hematology, urinalysis) | X | | | 0 | 24 ⁱ | | 0 | | | | 48 | | | | X |
| HBcAb, HBsAg, HCV, and HIV tests | X | | | | | | | | | | | | | | |
| Serum pregnancy test ^h | X | | | | | | | | | | | | | | |
| Urine pregnancy test ^h | | | X | | | | 0 | | 0 | | | | | | X |

| Visit | Screening | Treatment Period ^a | | | | | | | | Follow-Up ^a | | | | | |
|------------------------------|-----------|-------------------------------|----|----------------------------------------|-----------------|---|---|----|----------------------------------------|------------------------|----|----|----|----|------------|
| Study Day | ≤28 days | -2 | -1 | 1 ^b | 2 | 4 | 8 | 11 | 15 | 16 | 17 | 19 | 22 | 25 | 29/ EoS |
| FSH ^h | X | | | | | | | | | | | | | | |
| Drug and alcohol screen | X | X | | | | | | | | | | | | | |
| QuantiFERON®-TB Gold Plus | X | | | | | | | | | | | | | | |
| PK sampling: blood | | | | 0, 0.25, 0.5, 1, 2, 3, 4, 6, 8, 10, 12 | 24 ⁱ | 0 | 0 | 0 | 0, 0.25, 0.5, 1, 2, 3, 4, 6, 8, 10, 12 | 24, 36 | 48 | X | X | X | X |
| BTK occupancy | | | | 0, 1, 2, 4, 12 | 24 ⁱ | | 0 | | 0, 1, 2, 4, 12 | 24 | 48 | X | X | X | X |
| Skin inspection ^d | | | X | 0, 12 | 24 ⁱ | 0 | 0 | 0 | 0 | X | X | X | X | X | X |
| Non-PGx stored sample | | | | 0 | | | 0 | | | 24 | | | | | |
| PGx | | | | 0 | | | | | | | | | | | |

Abbreviations: AEs = adverse events; BTK = Bruton's tyrosine kinase; CRU = clinical research unit; ECG = electrocardiogram; EoS = end of study;

FSH = follicle-stimulating hormone; HBcAb = hepatitis B core antibody; HBsAg = hepatitis B surface antigen; HCV = hepatitis C virus; HIV = human immunodeficiency virus; IP= investigational product; PGx = pharmacogenomics; PK = pharmacokinetic; TB = tuberculosis.

Note: numbers are in hours in relation to dosing; 0 = predose.

- a All planned procedures will be done predose unless the time is indicated.
- b For twice-daily regimen, the time is based on the first dose. The second dose should be administered after sample collection for the 12-hour time point.
- c Subjects will be dosed every day from Day 1 through Day 15. For twice-daily regimen, only the morning dose will be administered on Day 15.
- d Assessment should be performed every day during the subject's stay at the CRU.
- e Height will be measured at screening only. Body weight will be measured in the morning.
- f Refer to Section 9.4.2 for instructions on vital signs.
- g Refer to Section 9.4.3 for instructions on ECGs. ECGs should be administered after subject has been resting in the supine position for approximately 5 minutes. On days without dosing, ECGs should be administered close to the Day 1 dosing time, when possible. ECGs will be collected in triplicate except at the screening visit.
- h All female subjects of childbearing potential will undergo a serum pregnancy test at screening. For women who are considered postmenopausal, FSH should be drawn to confirm postmenopausal status as defined in inclusion criterion [1b] and exemption from further pregnancy tests (urine) during the study.
- i This 24-hour sample is to be taken predose.

Study Schedule Protocol I8K-JE-JPDB (Cohorts 2, 3, and 4)

| Visit | Screening | Treatment Period ^a | | | Follow-Up ^a | | | | | |
|-------------------------------------------------------------------------|-----------|-------------------------------|----|-------------------------------------|------------------------|----|---|---|----|--------|
| Study Day | ≤28 days | -2 | -1 | 1 | 2 | 3 | 5 | 8 | 11 | 15/EoS |
| Inpatient stay at CRU | | ←—————→ | | | | | | | | |
| Informed consent | X | | | | | | | | | |
| Review eligibility | X | | X | | | | | | | |
| Randomization | | | | X | | | | | | |
| IP administration | | | | X | | | | | | |
| Complete medical history | X | | | | | | | | | |
| Review preexisting conditions/AEs | X | X | X | X | X | X | X | X | X | X |
| Review concomitant medications | X | X | X | X | X | X | X | X | X | X |
| Complete physical examination | X | | | | | X | | | | X |
| Symptom-directed physical examination | | X | X | X | X | | X | X | X | |
| Body weight and height ^b | X | | X | | | X | | | | X |
| Vital signs (pulse rate, blood pressure, body temperature) ^c | X | | 0 | 0, 1, 2, 4, 12 | 24 | 48 | | | | X |
| 12-Lead ECG ^d | X | | | -1, -0.5, 0, 0.5, 1, 2, 3, 4, 6, 12 | 24 | 48 | | | | X |
| Chest x-ray (posterior, anterior, and lateral) | X | | | | | | | | | |
| Clinical laboratory measures (serum chemistry, hematology, urinalysis) | X | | | 0 | | 48 | | | | X |
| HBcAb, HBsAg, HCV, and HIV tests | X | | | | | | | | | |
| Serum pregnancy test ^e | X | | | | | | | | | |
| Urine pregnancy test ^e | | | X | | | | | | | X |
| FSH ^e | X | | | | | | | | | |

| Visit | Screening | Treatment Period ^a | | | Follow-Up ^a | | | | | |
|---------------------------|-----------|-------------------------------|----|----------------------------------------|------------------------|----|---|---|----|--------|
| Study Day | ≤28 days | -2 | -1 | 1 | 2 | 3 | 5 | 8 | 11 | 15/EoS |
| Drug and alcohol screen | X | X | | | | | | | | |
| QuantiFERON®-TB Gold Plus | X | | | | | | | | | |
| PK sampling: blood | | | | 0, 0.25, 0.5, 1, 2, 3, 4, 6, 8, 10, 12 | 24, 36 | 48 | | X | | X |
| BTK occupancy | | | | 0, 1, 2, 4, 12 | 24 | 48 | | X | | X |
| Skin inspection | | | X | 0, 12 | X | X | X | X | X | X |
| Non-PGx stored sample | | | | 0 | | | | X | | X |
| PGx | | | | 0 | | | | | | |

Abbreviations: AEs = adverse events; BTK = Bruton's tyrosine kinase; CRU = clinical research unit; ECG = electrocardiogram; EoS = end of study;

FSH = follicle-stimulating hormone; HBcAb = hepatitis B core antibody; HBsAg = hepatitis B surface antigen; HCV = hepatitis C virus; HIV = human immunodeficiency virus; IP= investigational product; PGx = pharmacogenomics; PK = pharmacokinetic; TB = tuberculosis.

Note: numbers are in hours in relation to dosing; 0 = predose.

- a All planned procedures will be done predose unless the time is indicated.
- b Height will be measured at screening only. Body weight will be measured in the morning.
- c Refer to Section 9.4.2 for instructions on vital signs.
- d Refer to Section 9.4.3 for instructions on ECGs. ECGs should be administered after subject has been resting in the supine position for approximately 5 minutes. On days without dosing, ECGs should be administered close to the Day 1 dosing time, when possible. ECGs will be collected in triplicate except at the screening visit.
- e All female subjects of childbearing potential will undergo a serum pregnancy test at screening. For women who are considered postmenopausal, FSH should be drawn to confirm postmenopausal status as defined in inclusion criterion [1b] and exemption from further pregnancy tests (urine) during the study.

3. Introduction

3.1. Study Rationale

Study I8K-JE-JPDB (JPDB) is the first clinical evaluation of LY3337641 in Japanese subjects and is being conducted to assess the safety, tolerability, pharmacokinetics (PK), and pharmacodynamics (PD) of single-dose (SD) and multiple-dose (MD) administration of LY3337641 in healthy Japanese and Caucasian subjects. Findings from the study will be used to assess the safety and tolerability of LY3337641 in this study population including Japanese subjects, further characterize the PK properties of LY3337641, and explore the PD effects of Bruton's tyrosine kinase (BTK) inhibition. Such findings in Japanese subjects are essential for further clinical development in Japan for various indications.

3.2. Background

LY3337641 is an orally available, irreversible inhibitor of BTK, a member of the TEC family of cytoplasmic tyrosine kinases. BTK is a key signaling molecule in the B-cell-receptor and Fc-receptor pathways and an essential mediator of B-cell- and myeloid-cell-dependent inflammatory arthritis (Di Paolo et al. 2011; Chakravarty et al. 2013). BTK is primarily expressed in hematopoietic cells, including B cells, monocytes, and macrophages (Burger 2014). In humans, BTK loss-of-function mutations cause nonlethal X-linked agammaglobulinemia, resulting in reduced B-cell and immunoglobulin levels (Aalipour and Advani 2014).

LY3337641 is currently being developed for rheumatoid arthritis (RA), and a Phase 2 study in patients with RA (I8K-MC-JPDA [JPDA]) is ongoing. Potential therapeutic benefits of BTK inhibition for RA include reduced pathogenic B-cell autoantibody production and myeloid-cell proinflammatory cytokine production and inhibition of mast cell and basophil degranulation (Horwood et al. 2012).

LY3337641 demonstrates potent, irreversible BTK inhibition in BTK enzyme assays, cell-based BTK phosphorylation assays, and BTK occupancy assays.

The *in vivo* activity of LY3337641 was investigated in mouse and rat models of collagen-induced arthritis and mouse models of systemic lupus erythematosus. LY3337641 was effective in the mouse arthritis model, where it halted progression of clinical arthritis and significantly diminished structural damage in the joints. The high level of efficacy for clinical disease activity was reproduced in the rat arthritis model. LY3337641 was also effective in a spontaneous mouse model of systemic lupus erythematosus, where it improved skin lesions, reduced proteinuria, and improved renal histopathology scores. Taken together, these results suggest that LY3337641 may be useful for treatment of autoimmune diseases, including RA.

CCI

CCI

Results from nonclinical studies with LY3337641 and the Study JPDD safety profile support the design of this study.

3.3. Benefit/Risk Assessment

No clinically significant safety concerns have been identified at the doses proposed in this study for LY3337641. The dose levels included in this study are within the range of doses studied previously, and the tolerability has been confirmed.

More information about the known and expected benefits, risks, serious adverse events (SAEs) and reasonably anticipated adverse events (AEs) of LY3337641 are to be found in the Investigator's Brochure.

4. Objectives and Endpoints

Table JPDB.1 shows the objectives and endpoints of the study.

Table JPDB.1. Objectives and Endpoints

| Objectives | Endpoints |
|-------------------------------------------------------------------------------------------------------------------------------------------------------------------------------------------------------------------------------------------------------------------------------------------------------------------------------------------------------------------------------------------|---------------------------------------------------------------------------------------------------------|
| 
Primary To explore the safety and tolerability of LY3337641 in healthy Japanese and Caucasian subjects
 | AEs and SAEs |
| 
Secondary To estimate the PK parameters of single and multiple doses of LY3337641 following oral administration in healthy Japanese and Caucasian subjects
 | C _{max} and AUC |
| 
Exploratory Objectives 1. To explore the PD following single and multiple doses of LY3337641 in healthy Japanese and Caucasian subjects 2. To explore the safety, tolerability, PK, and PD of LY3337641 in Japanese subjects in relation to Caucasian subjects 3. To explore the effect of LY3337641 on ECG findings in healthy Japanese and Caucasian subjects
 | 
1. BTK occupancy 2. AEs, SAEs, C_{max}, AUC, and BTK occupancy 3. ECG parameters
 |

[figure not shown]
Abbreviations: AEs = adverse events; AUC = area under the plasma concentration-time curve; BTK = Bruton's tyrosine kinase; C_{max} = maximum drug concentration; ECG = electrocardiogram; PD = pharmacodynamics; PK = pharmacokinetic(s); SAEs = serious adverse events.

5. Study Design

5.1. Overall Design

This is a single-site, subject- and investigator-blind, randomized, placebo-controlled, SD and MD study to assess the safety, tolerability, PK, and PD of LY3337641 in healthy Japanese and Caucasian subjects. Subjects will be randomized to LY3337641 within each cohort as shown in [Figure JPDB.1](#). All cohorts will be randomized in a 3:1 ratio of LY3337641 to placebo. MD Cohort 1 (30 mg QD for 2 weeks) and Cohort 5 (optional) will consist of 12 subjects (8 Japanese and 4 Caucasian). SD Cohorts 2, 3, and 4 (5, 80, and 160 mg SD) will consist of 8 subjects (4 Japanese and 4 Caucasian). For each MD cohort, 6 Japanese subjects and 3 Caucasian subjects will receive LY3337641, while 2 Japanese subjects and 1 Caucasian subject will receive placebo. For each SD cohort, 3 Japanese subjects and 3 Caucasian subjects will receive LY3337641, while 1 Japanese subject and 1 Caucasian subject will receive placebo. Investigational product (IP) will be administered orally. Cohorts 1, 2, and 3 may be conducted in parallel if the site is able to accommodate more than 1 cohort at a time; however, priority will be given to dose Cohort 1, since the timing of this cohort will determine the timing of the interim analysis. Cohort 4 will be started based on the safety assessment up to Day 3 (48 hours postdose) of Cohort 2. If the dose level/regimen for Cohort 1 is not tolerated or there is a need to dose more subjects to assess safety, a daily dose of 30 mg or less (QD or BID) may be given in Cohort 5 based on the findings from Cohort 1. This will be discussed and agreed upon by the investigator and the Lilly clinical pharmacologist. The randomization rules and procedures will be the same as Cohort 1.

[Figure JPDB.1](#) illustrates the study design.

Abbreviations: BID = twice daily; FU = follow-up; JP = Japanese; LY = LY3337641; Pb = placebo; QD = once daily.

*Dose, regimen, and subject number may change for optional cohort.

Figure JPDB.1. Illustration of study design for Protocol I8K-JE-JPDB.

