7.1. Treatment Administered

This study involves a numerical comparison of LY3337641 (30 mg QD in MD cohorts and 5, 80, and 160 mg in SD cohorts) with placebo, when administered orally. The study drug is supplied as tablets containing 5 or 20 mg of LY3337641 with matching placebo tablets (Table JPDB.2).

LY3337641 and placebo will be administered orally with approximately 200 mL of room temperature water in the morning of each dosing day with the subject in a sitting position. Subjects will not be allowed to lie supine for 2 hours after dosing, unless clinically indicated or as needed for study procedures.

Table JPDB.2. Treatment Administered

| Cohort | Dose | Number of Tablets |
|----------|------------------|------------------------------------------------------|
| Cohort 1 | LY 30 mg QD | 1 x 20-mg LY tablet 2 x 5-mg LY tablets |
| | Placebo 30 mg QD | 1 x 20-mg placebo tablet 2 x 5-mg placebo tablets |
| Cohort 2 | LY 80 mg | 4 x 20-mg LY tablets |
| | Placebo 80 mg | 4 x 20-mg placebo tablets |
| Cohort 3 | LY 5 mg | 1 x 5-mg LY tablet |
| | Placebo 5 mg | 1 x 5-mg placebo tablet |
| Cohort 4 | LY 160 mg | 8 x 20-mg LY tablets |
| | Placebo 160 mg | 8 x 20-mg placebo tablets |

Abbreviations: LY = LY3337641; QD = once daily.

The investigator or designee is responsible for:

- explaining the correct use of the IP to the subject,
- verifying that instructions are followed properly,
- maintaining accurate records of IP dispensing and collection,
- and returning all unused medication to Lilly or its designee at the end of the study.

Note: In some cases, sites may destroy the material if, during the investigative site selection, the evaluator has verified and documented that the site has appropriate facilities and written procedures to dispose of clinical trial materials.

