7.4. Dose Modification

7.4.1. Dose Escalation

All doses in this study have been previously tested and shown to be well tolerated in Study JPDD. However, Japanese subjects have not received LY3337641 previously. The dose escalation decision will be made based on the safety data from both Japanese and Caucasian subjects up to Day 3 (48 hours postdose) of 80-mg SD administration (Cohort 2) to proceed to the 160 mg SD cohort (Cohort 4).

Safety data for the 80-mg SD will be the primary criteria for dose escalation to the 160-mg SD. In addition, if available at the time of dose escalation decision, PK (C_{max} , AUC, and clearance) results may be used as supporting data for dose escalation, but such data are not required. No dose escalation can occur without prior discussion and agreement between the investigator and the Lilly clinical pharmacologist or clinical research physician.

Safety data, in particular AEs, SAEs, and adverse laboratory abnormalities, will be independently assessed by the investigator and will be considered related to the IP, unless there is clear evidence that the event is not related.

After review of these data, an agreement on the appropriate dose escalation will be made by the investigator and sponsor for the 160-mg SD cohort. The magnitude of the dose escalation may be reduced following data review, but the highest SD will not exceed 160 mg.

If any of the following scenarios occur, dosing at the current level and further dose escalation will be stopped until the safety data can be reviewed:

- 1) 1 or more subjects experience an SAE
- 2) 2 or more subjects experience a clinically significant event that is related to LY3337641 administration
- 3) greater than 3 subjects at 1 dose level experience moderate treatment-related AEs that impair normal activities

After the safety review is completed, if Cohort 2 dosing has not been completed, dosing may resume if agreed upon by the investigator and sponsor. Once all data from Cohort 2 has been

obtained, an agreement on the appropriate dose escalation will be made by the investigator and sponsor for the 160-mg SD cohort or a lower dose.

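### Does the order of the single-dose list in Protocol 5.1 and SAP 5 leave it unclear which dose gates the 160 mg cohort?

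*Protocol*

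**What the plan says.** Protocol 5.1 and SAP 5 describe the single-dose part in the same words: "SD Cohorts 2, 3, and 4 (5, 80, and 160 mg SD) will consist of 8 subjects". A little later in the same paragraph both give the release condition for the top dose: "Cohort 4 will be started based on the safety assessment up to Day 3 (48 hours postdose) of Cohort 2". That sentence names a cohort and no dose. The paragraph also allows overlap: "Cohorts 1, 2, and 3 may be conducted in parallel if the site is able to accommodate more than 1 cohort at a time".

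Protocol 7.1 introduces the treatments as "30 mg QD in MD cohorts and 5, 80, and 160 mg in SD cohorts", without cohort numbers. Directly below, Table JPDB.2 pairs cohort and dose row by row: "Cohort 2 | LY 80 mg | 4 x 20-mg LY tablets" and "Cohort 3 | LY 5 mg | 1 x 5-mg LY tablet", with Cohort 4 at 160 mg.

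Protocol 7.4.1 sets the escalation rule. It bases the decision on safety up to 48 hours after "80-mg SD administration (Cohort 2) to proceed to the 160 mg SD cohort (Cohort 4"), and adds: "Safety data for the 80-mg SD will be the primary criteria for dose escalation to the 160-mg SD".

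SAP 6 labels the treatment groups by dose and gives no cohort numbers.

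**The concern.** Three cohort numbers followed by three doses invite matching in order. The sentence just before attaches 30 mg to Cohort 1 with the same bracket construction, and the last pair, Cohort 4 with 160 mg, agrees with Table JPDB.2. Nothing in the sentence warns that the other two pairs do not.

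The release sentence then leans on the number alone. This is the only stated escalation gate, and Protocol 7.4.1 notes that Japanese subjects had not received the drug before. Since Cohorts 1, 2 and 3 may overlap, the order of dosing does not show which dose Cohort 2 means. If the list order were the intended pairing, the gate in 5.1 and the gate in 7.4.1 would refer to different doses, and the release of 8 subjects (6 on active drug) would rest on whichever section the reader used.

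**Working it through.** **1. The plan's own size.** Cohort sizes come from Protocol 5.1: 12 per multiple-dose cohort and 8 per single-dose cohort.

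- Without optional Cohort 5: 12 + 3 × 8 = 36.
- With Cohort 5: 2 × 12 + 3 × 8 = 48.

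This reproduces the stated 36 to 48 completers. All three single-dose cohorts are the same size, so the totals do not depend on which number carries which dose.

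**2. List order against the table.** The table dose is tablets × strength.

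| Cohort | 5.1 and SAP 5, matched in order | Table JPDB.2 | Same? |
|---|---|---|---|
| 2 | 5 mg | 4 × 20 = 80 mg | no |
| 3 | 80 mg | 1 × 5 = 5 mg | no |
| 4 | 160 mg | 8 × 20 = 160 mg | yes |

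The tablet counts agree with the table's own doses, so the table is internally consistent. The labels differ for Cohorts 2 and 3: 2 × 8 = 16 subjects, of whom 2 × 6 = 12 are on active drug. On the list-order reading the step from Cohort 2 to Cohort 4 is 160/5 = 32-fold; on the table it is 160/80 = 2-fold.

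**3. Is the list a pairing?** Neither section says the doses are given respectively. The synopsis and Protocol 7.1 use the same ascending run of doses with no cohort numbers. In 7.1 it stands immediately above a table whose Cohort 2 row is 80 mg, so there it cannot be in cohort order. SAP 6 also lists the single doses in ascending order. Read as a set of three doses for three cohorts, the sentence agrees with Table JPDB.2 and with 7.4.1. Only the list-order reading creates a conflict, and no other statement in the text supports that reading.

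**4. Do the gate sentences agree?** Protocol 5.1 and 7.4.1 name the same gating cohort (2), the same released cohort (4) and the same time point (Day 3, 48 hours postdose). Section 7.4.1 adds the doses, and those match the table. No passage states that 5 mg data release the 160 mg cohort.

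**5. What else hangs on the cohort number?**

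- Cohorts 2, 3 and 4 share one Schedule of Activities and one blood-sampling table.
- Each has the same 3:1 allocation within each race.
- The planned interim analyses are triggered by Cohort 1.
- SAP 6 defines treatment groups by dose, and the power model in SAP 9.3.2 uses dose as its regressor.

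Exchanging the labels of Cohorts 2 and 3 would change none of these. Only the gate depends on the pairing, and 7.4.1 spells that out.

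**The case for a change.** The best argument for acting is that a safety gate should read the same wherever it appears. The SAP text has no counterpart to Table JPDB.2 or to Protocol 7.4.1, so from that text alone a reader cannot recover the pairing. The sponsor has also treated this kind of mismatch as worth correcting: Amendment (a) reworded a schedule footnote on Day 15 dosing because it did not match another section. The repair would be a few words.

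Part of this stands. The sentence in 5.1 is loosely written, and a hurried reader could be misled. But the SAP does not control dosing. SAP 3 says its design summary is there to help the reader, and it supersedes the protocol only on statistical considerations. Staff preparing doses work from a treatment table that is unambiguous. The escalation decision is taken under 7.4.1, which names the dose and requires prior agreement between the investigator and the sponsor's clinical pharmacologist or physician. The 32-fold step arises only on a reading that 7.4.1 excludes. The permitted overlap of Cohorts 1 to 3 is also an ordinary reason for cohort numbers not to follow dose order.

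**Conclusion.** No change is called for. This is a clerical looseness: an ascending list of doses set beside cohort numbers that do not run in dose order. Two of the three labels mismatch if the list is read in order; none do if it is read as a set. A team following the plan as written would dose from Table JPDB.2 and escalate under 7.4.1, and those two agree. The planned 36 to 48 completers, the data collected and every planned analysis are the same on either reading.

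The conclusion rests on two assumptions. The first is that 7.4.1 and Table JPDB.2, as the specific provisions, state what the sponsor intends; only the sponsor's clinical team can confirm the pairing, and this note does not judge which dose should gate which. The second is that Figure JPDB.1, which could not be checked, does not show a different pairing; if it does, the passages must be reconciled. Should the protocol be amended for another reason, putting the dose beside each single-dose cohort number in 5.1 and in the release sentence would be a reasonable courtesy to the reader.
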